13.4.2. Hypoglycemia Symptoms

Symptom relief will be analyzed as aggregate scores for the four autonomic symptoms, four neuroglycopenic symptoms, and 8 total (autonomic and neuroglycopenic) symptoms (see [Appendix 1](#)).

For analysis, “relief” will be defined as a return to a score no more than one unit above baseline symptoms during the euglycemic baseline period.

The time to the minimal score post baseline will be described and compared between the treatment groups using a mixed model with treatment, period and sequence as terms. Similarly, the time to first reporting of “no” for the overall hypoglycemia question (“Do you currently feel hypoglycemic?”) will be described and compared between the groups.

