5.3.6.2.3 Time-to-Event Efficacy Endpoints

Symptom relief will be analyzed as aggregate scores for the four autonomic symptoms, four neuroglycopenic symptoms, and 8 total (autonomic and neuroglycopenic) symptoms.

Symptom relief of hypoglycemia is defined as a return to a score (ANS, AAS, and ATS) no more than one unit above euglycemic baseline (1 / 2). Only subjects with baseline score at least 2 or more (for ANS, AAS, or ATS) will be evaluable for this analysis.

Complete resolution of hypoglycemia symptoms is defined as all symptoms in the domain (ANS, AAS, or ATS) have a score of 1 after receiving glucagon.

The time to resolution of the overall feeling of hypoglycemia is defined as first reporting of “No” for the global hypoglycemia question. This will be calculated as the difference (in mins) between the actual time when the first “No” for “Overall Assessment of Hypoglycemia” is observed and the time to decision of glucagon dosing.

Glucagon Preparation Time is defined as time to administer study drug from a decision to dose.

The following timing parameters will be calculated for analysis:

1. Time to a Positive Plasma Glucose Response (PGR) from injection of study drug.
2. Glucagon Preparation Time.
3. Time to symptom relief of autonomic and neuroglycopenic symptoms of hypoglycemia from a decision to dose. That include:
 - time to symptom relief of neuroglycopenic symptoms (ANS) from a decision to dose;
 - time to symptom relief of autonomic symptoms (AAS) from a decision to dose;
 - time to symptom relief of autonomic and neuroglycopenic symptoms (ATS) from a decision to dose;
4. Time to complete resolution of autonomic and neuroglycopenic symptoms of hypoglycemia from a decision to dose. That include:
 - time to complete resolution of neuroglycopenic symptoms (ANS) from a decision to dose;
 - time to complete resolution of autonomic symptoms (AAS) from a decision to dose;
 - time to complete resolution of autonomic and neuroglycopenic symptoms (ATS) from a decision to dose;
5. Time to minimal score of autonomic and neuroglycopenic symptoms of hypoglycemia from a decision to dose. That includes:
 - time to minimal score of neuroglycopenic symptoms (ANS) from a decision to dose;

- time to minimal score of autonomic symptoms (AAS) from a decision to dose;
 - time to minimal score of autonomic and neuroglycopenic symptoms (ATS) from a decision to dose;

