6. Time to resolution of the overall feeling of hypoglycemia from a decision to dose. The following rules will be applied:
- only subjects who answered “Yes” at baseline will be evaluable for this analysis;
 - in very rare cases, if subject answers “Yes” all the way to the last time point, the total time to the last assessment will be recorded.

Actual Time will be used for calculations.

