6.6.4 Time-to-Event Analyses

All the Time-to-Event Efficacy parameters will be presented descriptively.

A survival analysis will be conducted for comparing the difference between treatments.

Survival curves will be provided to compare both treatments graphically. Two-sided log-rank p-value for the difference will be reported.

This analysis will be repeated for ITT, mITT and PP population.

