10 DEVIATIONS FROM PLANNED ANALYSIS

For timing parameters mixed model analysis was replaced by time-to-event analysis.

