14.2.2.3.1	Non-inferiority Analysis of Time (min) to Symptom Relief (Neuroglycopenic, Autonomic and Total) After Decision to Dose by Population and by Treatment (All Enrolled Patients)
14.2.2.3.2	Non-inferiority Analysis of Time (min) to Complete Resolution (Neuroglycopenic, Autonomic and Total) After Decision to Dose by Population and by Treatment (All Enrolled Patients)

Tables	
Number	Title
14.2.2.3.3	Non-inferiority Analysis of Time (min) to Resolution of the Overall Feeling of Hypoglycemia After Decision to Dose by Population and by Treatment (All Enrolled Patients)
14.2.2.3.4	Non-inferiority Analysis of Time (min) to the Minimal Post Baseline Score After Decision to Dose by Population and by Treatment (All Enrolled Patients)
14.2.2.4	Non-inferiority Analysis of Glucagon Preparation Time (min) by Population and by Treatment (All Enrolled Patients)
14.2.2.5.1	Non-inferiority Analysis of Study Drug Assignment Questionnaire by Treatment (Per-Protocol Population)
14.2.2.5.2	Non-inferiority Analysis of Mean Visual Analog Scale (VAS) (Intent-to-Treat Population)
14.3.1.1	Overview of Adverse Events (Safety Population)
14.3.1.2.1	Summary of Treatment-Emergent Adverse Events by System Organ Class, Preferred Term and by Treatment (Safety Population)
14.3.1.2.2	Summary of Treatment-Emergent Adverse Events by System Organ Class, Preferred Term, Period and by Treatment Sequence (Safety Population)
14.3.1.3.1	Summary of Treatment-Emergent Adverse Events by System Organ Class, Preferred Term, Severity and by Treatment (Safety Population)
14.3.1.3.2	Summary of Treatment-Emergent Adverse Events by System Organ Class, Preferred Term, Severity, Period and by Treatment Sequence (Safety Population)
14.3.1.4.1	Summary of Treatment-Emergent Adverse Events by System Organ Class, Preferred Term, Relationship to Study Drug and by Treatment (Safety Population)
14.3.1.4.2	Summary of Treatment-Emergent Adverse Events by System Organ Class, Preferred Term, Relationship, Period to Study Drug and by Treatment Sequence (Safety Population)
14.3.1.5.1	Summary of Serious Adverse Events Leading to Study Discontinuation by System Organ Class, Preferred Term and by Treatment (Safety Population)
14.3.1.5.2	Summary of Serious Adverse Events Leading to Study Discontinuation by System Organ Class, Preferred Term, Period and by Treatment Sequence (Safety Population)

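### Time to minimal symptom score does not track benefit, so its planned comparison can favour the less effective drug or miss non-improvement

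*SAP*

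**What the plan says.** Item 5 of the timing parameters in SAP 5.3.6.2.3 is "Time to minimal score of autonomic and neuroglycopenic symptoms of hypoglycemia from a decision to dose". It is calculated separately for the average neuroglycopenic (ANS), autonomic (AAS) and total (ATS) scores. It comes from Protocol 13.4.2: "The time to the minimal score post baseline will be described and compared between the treatment groups using a mixed model". SAP section 10 changes the method: "For timing parameters mixed model analysis was replaced by time-to-event analysis".

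SAP 6.6.4 therefore applies survival curves and a log-rank test in the ITT, mITT and PP populations: "Two-sided log-rank p-value for the difference will be reported". SAP Appendix 1 adds table 14.2.2.3.4, whose title begins "Non-inferiority Analysis of Time (min) to the Minimal Post Baseline Score After Decision to Dose", and survival figures 14.2.5.5.1 and 14.2.5.5.2.

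Two nearby rules do not reach this parameter as they are placed:
- "Only subjects with baseline score at least 2 or more (for ANS, AAS, or ATS) will be evaluable for this analysis" follows the definition of symptom relief.
- For a subject who never stops feeling hypoglycemic, "the total time to the last assessment will be recorded", but that rule sits under the overall-feeling item.

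For item 5 itself, nothing says how much improvement is needed, which occurrence counts if the minimum recurs, or how a subject who does not improve is handled. The sample time-to-event code in SAP Appendix 2 has no censoring variable, so every recorded time counts as an event.

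**The concern.** Relief and complete resolution are tied to stated levels: within one unit of the euglycemic baseline, and all symptoms in the domain at 1. The minimal score is tied to nothing but the subject's own record. Every series of scores has a lowest value, so every subject with data has an event, including one who gained nothing. Anyone reading a survival curve will tend to take an early event as fast relief, and here it may mean no relief.

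Two features add to this. The clock starts at the decision to dose, and only one product is reconstituted after that decision (Protocol 9.3.3). For a subject who does not improve, the recorded time is then preparation time plus the interval to the first assessment. A preparation difference could appear as a symptom difference. Also, Protocol 7.1 expects symptoms in most subjects, not all, and no Gold scale score is exclusionary. With no evaluability rule for item 5, a subject without symptoms is also an early event.

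**Working it through.** The plan gives no figure for this parameter, so there is none to reproduce. The check applies the definition itself.

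**Step 1: what the definition measures.** Let S(t) be a subject's score at time t after injection and P the preparation time. Read as first occurrence:

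T = P + min{t : S(t) = lowest observed S}

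Adding a constant to S leaves T unchanged. If S(t) = S0 − k·g(t), T is the same for every k > 0 (ignoring the rounding of scores to whole numbers). So T carries no information on how far symptoms fell.

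**Step 2: fixed profiles.** The grid is from Protocol 10.2.1.2: every 5 minutes to 90, then 120, 150 and 180. The score range is 1 to 6 (Protocol Appendix 1). The profiles are illustrative. Times are from injection; P must be added to each.

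| Profile | First occurrence | Last occurrence |
|---|---|---|
| Flat at 3.0 | 5 min | 180 min |
| Worsening from 3.0 | 5 min | 5 min |
| 3.0, then 2.75 from 10 min on | 10 min | 180 min |
| Full recovery, 3.0 to 1.0 | 35 min | 180 min |
| No symptoms throughout | 5 min | 180 min |

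Under first occurrence, no benefit and worsening both come out 35 − 5 = 30 minutes earlier than full recovery. Under last occurrence, flat and full recovery tie at 180 minutes.

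**Step 3: effect on the log-rank test.** There were 111 subjects per drug (the evaluable target in SAP 4.2). Every time was an event and pairing was ignored, as in the sample code. The test was two-sided at 5%. Assumptions not in the documents: four items start at 2 to 4; responders decay towards 1 with a time constant of 8 to 20 minutes; non-improvers keep their starting level; item noise has SD 0 or 0.3; P is left out. All subjects on drug A respond. Drug B has the stated share of non-improvers.

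| Item noise SD | Non-improvers on B | Mean time A / B (min) | Test favours B (worse) | Test favours A (better) |
|---|---|---|---|---|
| 0 | 10% | 31.3 / 28.8 | 17% | 0% |
| 0 | 20% | 31.4 / 26.0 | 54% | 0% |
| 0 | 30% | 31.3 / 23.5 | 81% | 0% |
| 0 | 50% | 31.3 / 18.2 | 100% | 0% |
| 0.3 | 10% | 36.6 / 36.5 | 4% | 6% |
| 0.3 | 20% | 36.8 / 36.8 | 2% | 4% |
| 0.3 | 30% | 36.7 / 37.0 | 0% | 5% |
| 0.3 | 50% | 36.6 / 37.0 | 0% | 7% |

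There were 300 runs per row without noise and 101 with noise. At 5%, the simulation error with 101 runs is √(0.05 × 0.95 / 101) ≈ 2 percentage points. Chance alone gives 2.5% in each direction.

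**Step 4: sensitivity.** A second simulation of the same kind gave 18% and 82% in favour of the worse drug at 10% and 30% flat non-improvers, and 0 to 1.5% at noise SD 0.3. Another, at low rates, gave 4%, 7% and 17% at 2%, 5% and 10% flat non-improvers. With noise it gave 1 to 2% for the worse drug and 3 to 6% for the better one at those rates. At 50% non-improvers with noise, the better drug was favoured in 24% of runs and the worse in none.

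**The case against.** The strongest reply concerns direction and size. No document states that a shorter time is better. The log-rank test is two-sided, no margin is given, and the non-inferiority label also heads the tables for Tmax, preparation time, VAS and even the treatment-guess questionnaire. That stands: a favourable reading of short times is what a reader would infer, not a written rule.

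Second, reversal needs perfectly flat self-reported scores. An extreme construction, with full recovery at a mean of 30 minutes against a one-point drop by 10 minutes that then stalls, gives a log-rank |z| of about 14.6. It shows the mechanism but does not predict this trial. Both arms receive 1 mg of glucagon, and SAP 4.2 expects recovery close to 100%. This also stands, although that expectation concerns the glucose response rather than symptoms.

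Third, rescue glucose is possible at 30 minutes after a poor glucose response (Protocol 7.3). If later scores are kept, such a subject may reach the minimum late. If they are dropped, the minimum falls within about 30 minutes. SAP 4.1 ties censoring to an insulin restart while quoting protocol text that also covers other interventions, so the point is not settled.

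Fourth, a drug that failed to relieve symptoms would also show in the mean scores, relief, complete resolution and the symptomatic response rate. That limits the harm. None of these replies gives item 5 a link to benefit.

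**Conclusion.** The concern holds. Time to minimal score takes no account of how much symptoms improve, and it counts non-improvers as events. Under first occurrence, the planned comparison can favour the less effective drug when non-improvers' scores are flat. When scores fluctuate, it largely fails to detect non-improvement. Which applies depends on score behaviour that the documents do not describe; the percentages rest on the simulation assumptions listed above and on times counted from injection.

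A reader might go further and conclude that the weaker drug will win, or that this is the main symptom comparison. The documents support neither. Reversal vanished at item noise SD 0.3. Protocol 13.4.2 gives the parameter one sentence after defining relief, and it is absent from the numbered secondary endpoints in Protocol 5.3.2 and SAP 3.3.2. The effect is confined to a supportive parameter, and the primary analysis is untouched. The change is still worth making, because the stated analysis cannot answer a question about benefit.

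**What to change.** 1. Remove the log-rank comparison, table 14.2.2.3.4 and figures 14.2.5.5.1 and 14.2.5.5.2 for time to minimal score.
2. Keep at most a descriptive summary (tables 14.2.1.3.5.x). State the first-occurrence rule and show the minimal score reached beside the time.
3. Base between-treatment inference on symptom timing on relief and complete resolution, which have fixed thresholds. Censor subjects who never reach the threshold at their last assessment, and add a censoring variable to the time-to-event code in SAP Appendix 2.
4. Optionally, compare the mean change in ANS, AAS and ATS from the last score before injection, over 0 to 30 and 0 to 90 minutes, using the crossover mixed model already in SAP 6.6.2.

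The cost is SAP wording, an entry in SAP section 10, and alignment of Protocol 13.4.2. One inferential comparison named in that protocol section is lost. No listed secondary endpoint is lost, and no new data are needed.

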Plasma glucose levels will be monitored for 180 minutes post-dosing. It is believed that plasma glucose < 54 mg/dL (< 3 mmol/L) will be low enough to generate neuroglycopenic and autonomic symptoms in most subjects, yet high enough (i.e., > 42 mg/dL [> 2.33 mmol/L])) to avoid the impairment of consciousness. Consequently, subjects will complete a questionnaire about symptoms of hypoglycemia [Nerموen] during the hypoglycemia induction phase, and for 180 minutes after treatment with glucagon.

After a wash-out period of 7 to 28 days, subjects will return to the CRC and the procedure will be repeated with each subject crossed over to the other treatment.

After study-related procedures are performed on each of the treatment days (see Table 5), subjects will be discharged after consuming a meal as per each site's usual practice. A follow-up visit as a safety check will be conducted 2 to 7 days after administration of the final dose of study drug.

The last subject last visit (LSLV) for each site is defined as the date the last subject completes the Follow-Up Visit (Visit 4), with the understanding that final review by the Investigator may be delayed a few days to allow for receipt of final lab results. The end of the trial is the date of the LSLV for the last site.

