5. Subcutaneous administration of the study drug will be made to the abdomen around the umbilicus as per [Section 9.3.3](#). Clock time of study drug administration will be recorded in the source documents. After study drug injection, the study product will be disposed in a location away from the subject in a manner that maintains the blind. After disposal, the blindfold and headphones will be removed from the subject.
6. Following study drug administration, plasma glucose will be measured every 5 ± 2 minutes through 90 minutes, and every 30 ± 2 minutes thereafter through 180 minutes post-dosing.

7. At 180 minutes post-dosing, the subject will resume insulin therapy and be given a meal as per the standard practice at each site. The subject can be discharged from the clinic if their plasma glucose is >100 mg/dL (> 5.55 mmol/L) and the subject is deemed medically stable.
8. After study drug administration and before 180 minutes post-dosing, if rising glucose levels are observed and if deemed medically necessary, insulin therapy or other medical intervention may be initiated by the Investigator.
 - a. Such intervention is not recommended to occur before 90 minutes post-dosing of study drug.
 - b. Plasma glucose data and assessments of neuroglycopenic symptoms will be censored after the time of intervention, per the statistical analysis plan.
 - c. These interventions (such as insulin, carbohydrates, or a meal) prior to 180 minutes post study drug administration should be captured in the source documents, and further glucose measurements may be performed at the discretion of the Investigator.

Hypoglycemia Symptom Assessments

Subjects will complete a questionnaire regarding severity of hypoglycemia symptoms ([Appendix 1](#)) at the following time points:

1. Just before the IV bolus push dose of insulin is given at the start of the hypoglycemia induction procedure (baseline),
2. Every time blood is drawn for evaluation of plasma glucose concentration during the induction procedure,
3. Just before study drug is administered,
4. Every 5 ± 2 minutes after glucagon is administered until 90 minutes post-dosing, and every 30 minutes (coinciding with plasma glucose measurements) between 90 and 180 minutes post study drug administration.

Local Tolerability and Adverse Events

Local tolerability and AEs will be assessed as follows:

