RUN-IN 1 and RUN-IN 2 analysis phases will include all interventions before dose injections, thereof:

- EUGLYCEMIC BASELINE 1 / 2.

The Euglycemic Baseline phase will be determined as time interval which starts from last 30 minutes of the baseline euglycemic steady state period, covering at least 3 scheduled consecutive plasma measurements in the target range at 0, 15, and 30 minutes used to confirm euglycemic steady state; and stops just before hypoglycemia induction with IV bolus push dose.

Euglycemic Baseline (1 and 2): to determine for the Hypoglycemia Symptoms Assessment scheduled at the end of this phase just before the IV bolus push dose of insulin, will serve as baseline to determine hypoglycemia symptoms relief and/or resolution within Treatment Period (1 and 2). If more than one assessment is performed in this time interval, then the last assessment of each hypoglycemia symptom or score will be selected for use as the baseline.

- HYPOGLYCEMIA INDUCTION (1 and 2). During the induction procedure the subject will enter a state of hypoglycemia through the administration of regular insulin diluted in normal saline within a controlled and monitored setting.

Hypoglycemic steady state (1 and 2): for Treatment Period (1 and 2) is confirmed if:

- penultimate plasma glucose measurement during hypoglycemia induction is < 54.0 mg/dL (< 2.78 mmol/L);
- last plasma glucose measurement during hypoglycemia induction is ≥ 42 mg/dL (≥ 2.33 mmol/L) and < 54 mg/dL (< 2.78 mmol/L); and
- 8-minute linearly extrapolated value from two last measurements of plasma glucose is ≥ 42 mg/dL (≥ 2.33 mmol/L).

Hypoglycemic Baseline (1 and 2). If the subject achieved hypoglycemic steady state then from the last of the last two plasma glucose readings during hypoglycemia induction to time of study drug administration will be defined as Hypoglycemic Baseline for the corresponding treatment period and will serve as baseline for the Primary Endpoint and Secondary Endpoints related to pharmacokinetic and pharmacodynamic characteristics within Treatment Period (1 and 2).

Assessments and Adverse Events with onset in TREATMENT PERIOD 1 or TREATMENT PERIOD 2 will be attributed to the actual treatment and analyzed respectively. Adverse

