6.2 Euglycemic Baseline

Prior to starting the hypoglycemia induction procedure, the subject must have stable plasma glucose for at least 30 minutes at 95 ± 20 mg/dL (75 to 115 mg/dL [4.17 to 6.38 mmol/L]) at a stable IV insulin infusion rate varying no more than $\pm 20\%$ during which plasma glucose must be measured at least every 15 ± 2 minutes (i.e., at least 3 consecutive values in the target range at 0, 15, and 30 minutes).

For Hypoglycemia Symptoms Assessment scheduled at the end of the Euglycemic Baseline phase just before the IV bolus push dose of insulin, will serve as baseline to determine hypoglycemia symptoms relief and/or resolution. If more than one assessment performed in this time interval, then the last assessment of each hypoglycemia symptom or score will be selected for baseline.

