6.3 Hypoglycemic Baseline

Hypoglycemic steady state is defined as a confirmatory plasma glucose value ≥ 42 mg/dL (≥ 2.33 mmol/L) and < 54 mg/dL (< 3 mmol/L), and an 8-minute linearly extrapolated future plasma glucose value ≥ 42 mg/dL (≥ 2.33 mmol/L).

To determine whether a hypoglycemic steady state has been achieved, confirmatory plasma glucose measurements will be taken as necessary at 5, 10 and 15 minutes after an initial plasma glucose < 54 mg/dL (< 3 mmol/L). Depending on the outcome, the following procedures will be followed.

1. If any of the confirmatory measurements meets the criteria for hypoglycemic steady state, the subject will be eligible to receive study glucagon, and further confirmatory plasma glucose measurement are not required.
2. If the final confirmatory plasma glucose value is < 42 mg/dL (< 2.33 mmol/L), the procedure will be terminated, study glucagon will NOT be administered, and the visit will be rescheduled after a minimum 3-day wait. At the Investigator's discretion, the subject should be treated with IV glucose or oral carbohydrates, it should be verified that the subject achieved a euglycemic state and is medically stable prior to discharge.
3. If any of the confirmatory plasma glucose measurements are > 54 mg/dL (> 3 mmol/L), then the IV insulin infusion will be re-started, and insulin adjustments will be made as per the induction procedure. Once another initial plasma < 54 mg/dL (< 3 mmol/L) is obtained, the sequence of up to 3 confirmatory plasma glucose readings will repeated.

If the subject achieved hypoglycemic steady state their linearly extrapolated plasma glucose value from the last two readings of hypoglycemia induction to time of study drug administration will be defined as Hypoglycemic Baseline for corresponding treatment period and will serve as baseline for the Primary Endpoint and Secondary Endpoints related to pharmacokinetic and pharmacodynamic characteristics within Treatment Period 1 / 2.

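### The evaluability rule for time to resolution of the feeling of hypoglycemia uses an unqualified baseline, and the only baseline the SAP defines for that questionnaire is the euglycemic one taken before induction

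*SAP*

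**What the plan says.** Endpoint 9 is timed from the decision to dose. SAP 5.3.6.2.3 states: "The time to resolution of the overall feeling of hypoglycemia is defined as first reporting of" No to the global question. It then admits only subjects who answered Yes "at baseline will be evaluable for this analysis". SAP 5.3.6.2.2 uses the same unqualified term when it counts subjects by a Yes or No answer at baseline.

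SAP 6.2, repeating 5.2, sets the symptom baseline at the end of the euglycemic phase. The assessment "just before the IV bolus push dose of insulin, will serve as baseline to determine hypoglycemia symptoms relief and/or resolution". Protocol 10.2.1.2 (Hypoglycemia Symptom Assessments) also labels the pre-bolus questionnaire as baseline. It lists a later questionnaire, completed shortly before injection, without that label.

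The SAP's other efficacy baseline, the Hypoglycemic Baseline of section 6.3, is an extrapolated plasma glucose value that "will serve as baseline for the Primary Endpoint and Secondary Endpoints related to pharmacokinetic and pharmacodynamic characteristics within Treatment Period 1 / 2".

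Protocol 13.4.2 describes time to the first No without any baseline restriction. The restriction appears only in the SAP, which takes precedence (Protocol 13.1, SAP 2).

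**The concern.** Endpoint 9 should show how quickly the feeling of induced hypoglycemia clears after glucagon. A subject can contribute only if that feeling is present when the clock starts. The eligibility test should therefore look at the answer after induction has taken effect.

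Read with the SAP's own definitions, the test looks at the answer before induction begins. It would retain people who felt hypoglycemic while euglycemic and remove people who first felt so during induction. The log-rank comparison, planned for the ITT, mITT and PP populations (SAP 6.6.4), would then describe a small and unrepresentative group, or could not be run. If a different baseline was meant, the choice is left to whoever programs the analysis, possibly after the data have been seen.

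**Working it through.** **Which baseline applies?** The candidates in the SAP are:

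| Baseline | Time point | Stated use | Fits a Yes/No answer? |
|---|---|---|---|
| Overall Baseline; Baselines 1 and 2 (5.2) | Screening to Day -1 check-in | Safety assessments | Not for this endpoint |
| Euglycemic Baseline 1 and 2 (5.2, 6.2) | Last assessment before the insulin bolus | Symptom relief and/or resolution | Yes |
| Hypoglycemic Baseline 1 and 2 (5.2, 6.3) | End of induction | Primary, PK and PD endpoints | No; 6.3 makes it an extrapolated glucose value |

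The global question is part of the same questionnaire (Protocol Appendix 1, SAP 5.3.6.2.2), and endpoint 9 is a time to resolution. Only the euglycemic row fits by definition.

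**What answer is expected there?** For the euglycemic phase, SAP 6.2 requires that "the subject must have stable plasma glucose for at least 30 minutes at 95 ± 20 mg/dL", that is, 75 to 115 mg/dL. Protocol 7.1 expects that glucose below 54 mg/dL "will be low enough to generate neuroglycopenic and autonomic symptoms in most subjects". That level is reached only through induction. A No at the euglycemic assessment is therefore the natural expectation. This is an inference; the documents give no rate.

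**Illustrative size.** The plan states no sample size, power or Yes rate for endpoint 9, so there is no figure to reproduce. The one document input is 111 subjects planned to be evaluable in both periods (Protocol synopsis, SAP 4.2). Every Yes rate p below is an assumption.

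- Evaluable subjects per treatment: n = 111 × p.
- Minimum detectable hazard ratio at 80% power and two-sided 0.05, by Schoenfeld's formula: HR = exp[(1.960 + 0.842) / √(d/4)], with d = 2n. This counts every evaluable record as an event and treats the two treatments as independent, as the log-rank code in SAP Appendix 2 does.

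| Baseline used | Assumed p | n per treatment | d | Detectable HR |
|---|---|---|---|---|
| Euglycemic | 0% | 0 | 0 | no analysis |
| Euglycemic | 5% | 5.6 | 11.1 | 5.4 |
| Euglycemic | 10% | 11.1 | 22.2 | 3.3 |
| Euglycemic | 20% | 22.2 | 44.4 | 2.3 |
| After induction | 70% | 77.7 | 155.4 | 1.57 |
| After induction | 90% | 99.9 | 199.8 | 1.49 |

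For example, at 10%: √(22.2/4) = 2.356, 2.802/2.356 = 1.189, exp(1.189) = 3.28.

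**Which assessment after induction?** The clock for endpoint 9 starts at the decision to dose. Study drug preparation begins only after that decision (Protocol 9.3.3, 10.2.1.2). GlucaGen Hypokit must be reconstituted and G-Pen need not be. An answer given just before injection therefore falls after time zero, at the end of an interval that can differ by product. Protocol 10.2.1.2 also has the questionnaire completed at every glucose draw during induction, so an answer with the confirmatory draw, at or before time zero, should exist for every dosed subject.

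**The case against.** The strongest reply is that the rule never says euglycemic. Where SAP 5.3.6.2.3 means that baseline it says so, in the definition of symptom relief, and then uses the bare word in the next sentence. The surrounding text points to a start near dosing: the item is analyzed from the decision to dose, and answering Yes through to the last time point is treated as very rare. The global question is also a separate Yes/No block, not one of the scored symptoms. This stands as evidence of intent. It does not supply a definition, because no symptom baseline near dosing appears anywhere in the SAP.

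A reader might infer that endpoint 9 will lose nearly all its subjects. The documents do not support that as a fact. The loss occurs only if the written definition is programmed, and its size rests on an assumed Yes rate. Nor is it established that most of the trial would be evaluable after induction. Protocol 7.1 states a belief about symptoms, not about the global question, and subjects with hypoglycemia unawareness are not excluded (Protocol 10.1, Appendix 4).

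The impact is also bounded. The endpoint plays no part in the non-inferiority decision. The item is summarized by time point, and the questionnaire is listed, whatever baseline is chosen.

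**Conclusion.** The concern holds as a wrong or undefined baseline reference in a stated rule for a named secondary endpoint. Applied with the SAP's own definitions, the rule selects on the euglycemic answer and excludes the subjects the endpoint is meant to describe. The likely intent was different, but the text does not carry it.

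The size is conditional. If 0 to 10% answer Yes at euglycemia, 0 to about 11 of 111 subjects per treatment remain. With 70 to 90% answering Yes after induction, about 78 to 100 would remain. Both ranges are assumptions. No stored data are lost and the primary conclusion is untouched, so this is a correction that should be made before database lock, not a threat to the trial.

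**What to change.** In SAP 5.3.6.2.2 and 5.3.6.2.3, define baseline for the overall hypoglycemia question, separately for each period, as the last questionnaire answer at or before the decision to dose. This will normally be the one completed with the confirmatory glucose draw. Using the questionnaire taken just before injection is tempting, but it would make inclusion depend on a response given after time zero, during a preparation interval that differs by product.

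In the same edit, name the baseline intended in the SAP 5.3.6.2.3 rule requiring a baseline score of at least 2 for symptom relief, which has the same ambiguity.

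The cost is SAP wording and the matching programming specification. The answers are already collected; no new data, visits or procedures are needed.
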